## **12 SAFETY ANALYSES**

All safety analysis will be carried out using the safety population and the subject's actual treatment received.

January 17, 2019

## 12.1 Adverse Events

A TEAE is defined as an adverse event that starts on or after the date of study drug IV infusion. AEs that start on the day of infusion will be classified as TEAEs if the "Same day as infusion" question is answered as "Started after the infusion." All AEs will be coded using MedDRA version 20.1.

An overall summary of AEs and TEAEs will be presented by treatment group, including the combined low-dose and high-dose VIS410, and overall subjects, with subject counts and percentages of subjects with the event. This summary will include subjects with any AE, any treatment-related AE, any TEAE, any treatment-related TEAE, any serious TEAE, any treatment-related serious TEAE, any TEAE of special interest (AESI), hypersensitivity reaction, anaphylactic reaction, any injection site AE, TEAEs by intensity, any moderate TEAE, any severe TEAE, TEAEs leading to study infusion discontinuation, treatment-related TEAEs leading to study infusion discontinuation, TEAEs leading to death, and treatment-related TEAEs leading to death. The difference in proportions between treatment groups in each of these categories will be calculated.

TEAE definitions:

- All AESIs will be defined by the eCRF field event type - AESI
- Injection site AEs will be defined by the eCRF field event type - injection site AE
- Treatment-related AEs will be defined by the investigators determination of the relationship as a reasonable possibility.
- 
- Anaphylaxis and hypersensitivity reactions will be determined by clinical evaluation of TEAEs per the Safety Plan prior to database lock. For input into analysis, a spreadsheet of subjects meeting the definition of either or both of these types of events will be generated and finalized prior to database lock.
- TEAEs leading to study infusion discontinuation will be defined by an answer of permanently discontinued as the eCRF action taken for an AE during infusion.

This summary will also be presented by region: North America (Canada and US), South Africa, Asia and Oceania (Australia, Malaysia, New Zealand, Singapore, and Thailand), and Europe (Belarus, Belgium, Bulgaria, Estonia, France, Georgia, Latvia, Russia, Serbia, Spain, Ukraine and Georgia))

A summary table by treatment group will present the number and percentage of subjects with TEAEs by SOC and SOC/PT. Subjects with multiple TEAEs within an SOC or SOC/PT combination will be counted only once for that SOC or SOC/PT combination. This table will also present a summary of subjects with any TEAE.

Similar summaries will be presented for Serious TEAEs, AESIs, injection site TEAEs, treatment-related TEAEs, TEAEs leading to study infusion discontinuation, TEAEs leading to death and TEAEs occurring in at least 5% of the subjects in any treatment group. The TEAE definitions for these tables will be the same as used in the overall summary of TEAEs.

January 17, 2019

A summary table by treatment group will be presented summarizing the intensity (mild, moderate, or severe) associated with each SOC and SOC/PT. A subject will be counted only once for an SOC or an SOC/PT combination. If a subject experiences multiple events in the same SOC or SOC/PT the highest recorded intensity will contribute counts to the summary table.

A summary table, by treatment group, will be presented for the TEAE relationship (reasonable possibility or no reasonable possibility) associated with each SOC and SOC/PT. A subject will be counted only once for an SOC or an SOC/PT combination. If a subject experiences multiple events in the same SOC or SOC/PT the closest relationship to study drug will contribute counts to the summary table.

All adverse event data will be listed by subject (in order of adverse event start date).

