9.1.8 Treatment-Emergent Adverse Event

A treatment-emergent adverse event (TEAE) is defined as any event not present prior to the initiation of the treatments or any event already present that worsens in either intensity or frequency following exposure to the treatments.

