9.4 Action Taken Regarding Investigational Product

The action taken toward the study drug must be described as one of the following:

- Permanently discontinued
- Stopped temporarily
- Modified infusion rate
- No action Taken
- Not applicable

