## **8 TREATMENT EXPOSURE AND COMPLIANCE**

The duration of infusion in minutes and volume of infusion in mL will be summarized by treatment group with n, mean, SD, median, minimum and maximum in the Safety and MITT populations. The number and percentage of subjects in each treatment group who received diphenhydramine per protocol, received an NSAID per protocol, had an infusion interruption of > 15 minutes, and did not receive the full infusion will also be summarized in the Safety and MITT populations. If there are a large number of interruptions (10% or more), incomplete infusions, or subjects not receiving the protocol-specified pre-treatment medications, the duration of infusion and volume of infusion summaries may be repeated with subsets based on these dosing parameters. The decision to generate any subset summaries will be made before unblinding the study.

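### Applied literally, SAP 12.1's infusion-day rule drops AEs that begin during the infusion from the TEAE tables, against the SAP's own date rule and protocol 9.1.8

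*SAP*

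**What the plan says.** SAP 12.1 opens with a date-level definition: an AE is treatment-emergent if its start date is the infusion date or later. The next sentence deals with the infusion day itself. AEs starting that day "will be classified as TEAEs if the 'Same day as infusion' question is answered as 'Started after the infusion". The section does not list the other possible answers or say how they are classified.

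Two later bullets in SAP 12.1 depend on this status. TEAEs leading to infusion discontinuation are identified by an answer of "permanently discontinued as the eCRF action taken for an AE during infusion". For the reactions of most interest with an antibody infusion, "Anaphylaxis and hypersensitivity reactions will be determined by clinical evaluation of TEAEs per the Safety Plan prior to database lock".

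Protocol 9.1.8 defines a TEAE as "any event not present prior to the initiation of the treatments or any event already present that worsens" in intensity or frequency after exposure. Protocol 10.7.1 likewise counts AEs whose onset falls in the treatment phase.

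On intensity, the by-intensity table described in SAP 12.1 (Table 14.3.1.12) has three categories: mild, moderate and severe. Protocol 9.2 requires a four-grade scale, with Grade 4 for life-threatening events.

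**The concern.** On Day 1 an AE can begin before, during or after the infusion. Protocol 9.6 records AEs from dosing with any study treatment, and protocol 7.5 gives the pretreatment about an hour before the infusion. A same-day question is therefore needed to separate earlier onsets from treatment-emergent ones. The SAP gives a status to only one answer, and its wording points to the period after the infusion, not the period after it starts.

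TEAE status feeds the summaries of serious events, AESIs, SOC and preferred term, relatedness and intensity, as well as the anaphylaxis and hypersensitivity review. Protocol 1.5.1.1 names serious infusion reactions, including anaphylaxis, as a class risk, and protocol 6.5.1 requires observation while the infusion runs. If onsets in that window were left out and were caused by the drug, the loss would fall mainly on the VIS410 arms and would understate the difference from placebo.

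**Working it through.** The plan gives no figure to reproduce, so the check is mainly of text.

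1. **The two SAP sentences.** The date-level sentence alone makes every infusion-day AE a TEAE, including one that begins during the infusion. If the same-day sentence only named one sufficient condition, it would add nothing to the first. It has a function only if it narrows the first, and read that way it keeps only AEs with the started-after answer.

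2. **Against protocol 9.1.8.** The reference point there is initiation of the treatments. An AE first seen during the infusion was absent before the infusion began, so it qualifies. The same-day sentence, read literally, leaves it out.

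3. **Against the SAP's own discontinuation bullet.** That bullet calls an AE during the infusion a TEAE when the infusion is permanently stopped, so the intent is evidently to count such events. It does not extend to the other actions in protocol 9.4, such as "Stopped temporarily" and "Modified infusion rate", or to AEs with no action taken. SAP 8 expects some interruptions, since it counts subjects who "had an infusion interruption of > 15 minutes". An AE behind a temporary stop has no stated status.

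4. **Blank answers.** SAP 4.2 moves some partial onset dates to the first treatment date, on a deliberately conservative principle. That is the day on which the same-day question decides, and SAP 12.1 gives no default if the question is unanswered.

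5. **Evidence on onset during the infusion.** It points both ways.
   - In the first challenge cohort, without pretreatment, 6 of 7 VIS410 subjects and 0 of 5 placebo subjects had GI symptoms. Most symptoms arose during the infusion or within 30 minutes of its end (protocol 1.3.2.2). The split is not given, so between 0 and 6 of the 7 could have had onset during the infusion.
   - In VIS410-102, one of 12 pretreated subjects at 3800 mg (1/12 = 8.3%) stopped the infusion for nausea, vomiting, chills and hot flashes (protocol 1.3.3 and 1.3.3.1). The discontinuation bullet would already treat that type of event as a TEAE.
   - On the other side, the GI onsets whose time is given after diphenhydramine plus ibuprofen or aspirin were at about 7 to 22 hours (protocol 1.3.2.2 and 1.3.3.1). VIS-C001 reported no infusion-related reactions, and its diarrhea began about 2 to 4 hours after dosing (protocol 1.3.1.2).

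6. **Scale per reclassified subject,** with the planned 40 per arm and 80 on VIS410:
   - One arm: 1/40 = 2.5 percentage points.
   - Pooled VIS410: 1/80 = 1.25 percentage points.
   - Threshold tables (14.3.1.4.1 and 14.3.1.4.2): 2/40 = 5.0% just meets the 5% threshold and 1/40 = 2.5% does not. At the 2% threshold, 1/40 = 2.5% is enough. One subject can therefore decide whether a term appears in either table.

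7. **Intensity.** Protocol 9.2 has Grades 1 to 4, and the by-intensity table has three categories. A Grade 4 TEAE would be either omitted or merged into severe, and the SAP does not say which. The overall summary lists TEAEs by intensity without naming categories, so it may or may not include Grade 4.

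**The case against.** The strongest reply is that the SAP's first sentence already covers these events, and that the second uses a plain condition rather than an exclusive one. The discontinuation bullet shows what was meant, and the started-after answer may simply mean after the start. The options in eCRF version 4.0 are not in the documents, so no loss can be demonstrated. This reply stands in part. It rules out saying that the SAP has no rule for such events, and it means the effect may be nil. It does not remove the contradiction, because a programmer following the specific sentence over the general one would exclude them.

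A reader might also draw stronger conclusions that the documents do not support:

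- **That infusion reactions would disappear from the report.** The any-AE and any-treatment-related-AE rows and the listings do not depend on TEAE status, and the overall row for injection-site AEs is worded without it. The hypersensitivity review also follows a Safety Plan that is not supplied.
- **That the share of observation time spent on infusion measures the share of events lost.** It says nothing about event risk.
- **That the protocol 11.4 dosing pause for severe GI TEAEs is affected.** That rule is in the protocol, which has its own TEAE definition. Nothing says that the SAP's programming rule would govern it.
- **That every serious event is Grade 4.** Appendix 14.3 says so, but protocol 9.2 calls such an event an SAE, and the appendix lets protocol-specific criteria override its table. A serious Grade 3 event has a category: severe.

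It is also fair to say that protocol 9.1.8 does not define which treatments it means. Anchoring at the start of the VIS410/placebo infusion is a sensible choice, but the protocol does not spell it out. If pretreatment is included, the starting point is earlier still, so onset during the infusion qualifies either way.

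**Conclusion.** The point holds as an internal contradiction in a stated safety rule. SAP 12.1's same-day sentence, applied literally, excludes AEs with onset between the start and the end of the infusion. Its opening sentence, its discontinuation bullet and protocol 9.1.8 all include them. The number affected cannot be estimated from the documents and is zero if the eCRF answer means after the start. If any are affected, each subject is worth 2.5 percentage points in an arm of 40, in tables that carry the main safety comparison. The missing Grade 4 category is a separate, smaller mismatch. Both should be corrected before unblinding. Neither affects the efficacy analysis or the data collected.

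**What to change.** In SAP 12.1, before unblinding:

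- State that an infusion-day AE with onset at or after the start of the VIS410/placebo infusion is a TEAE.
- List every answer to the same-day question and give each a TEAE status, with onset during the infusion counted as yes.
- Count a blank same-day answer as a TEAE, in line with the conservative approach of SAP 4.2.
- Add a Grade 4 (life-threatening) category to Table 14.3.1.12, and confirm that the by-intensity row of the overall summary includes it.

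The cost is a few lines of SAP text and minor reprogramming, with no new data. The small downside is that a few events that truly began before the infusion may be counted as TEAEs, in all arms.

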9.1.2 Signs and Symptoms of Influenza vs Adverse Events

The solicited and unsolicited signs and symptoms of influenza will not be reported as AEs as these constitute an endpoint of the study and will be recorded as such.

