9.1.3 Adverse Event of Special Interest

An adverse event of special interest (AESI; serious or non-serious) is one of scientific and medical concern specific to the Sponsor's product or program, for which ongoing monitoring by the Sponsor may be warranted. Such an event should be entered into EDC in a timely manner and if applicable, reported as an SAE. Depending on the nature of the event, rapid communication by the trial Sponsor to other parties (eg, regulators) might also be warranted (based on CIOMS VI).

For VIS410, the AESIs include the following:

- Abdominal cramping
- Diarrhea/Loose stool
- Nausea
- Vomiting
- Pruritus
- Rash
- Hypotension
- Throat tightening
- Trouble breathing or wheezing

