10.7.1 Adverse Events

The original terms in the electronic data capture (EDC) system used by Investigators to identify AEs other than symptoms of influenza A will be fully described and coded according to the Medical Dictionary for Regulatory Activities (MedDRA). The reported AEs will be allocated to phases based on their start date. All AEs will be listed. All AEs with onset during the treatment phase (ie, treatment-emergent AEs [TEAEs]) will be summarized.

AEs will be summarized overall and by treatment group and by MedDRA body organ system and preferred term, severity, relatedness, and seriousness.

The difference in proportions of subjects with AEs, TEAEs, hypersensitivity reaction, anaphylactic reaction, AESIs, and SAEs between treatment groups will be calculated.

Special attention will be paid to those subjects who died, discontinued due to an AE, or experienced a severe or serious AE. Summaries, listings, and narratives will be provided, as appropriate.

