**Changes from Previous Version of SAP**

SAP Version	Change from Previous Version	Reason	Revised SAP Sections
2.0	Population for Disposition Table 14.1.1.1 Changed from Enrolled to ITT	Change in analysis population	5.3, Appendix 16.6.1
	Details added regarding definition of baseline positivity based on viral load	Clarification of existing text	4.3, 9.2.10
	Addition of analysis based on mean VAS scores (summary table and figure) overall and in subsets based on time between symptom onset and treatment	Sponsor request	2.4.3, 3.3, 9.2.5
	Additional Subgroup added based on time between onset of symptoms and treatment	Subgroup for analysis of VAS scores	4.3
	Pairwise t-tests replaced by ANOVA based on ranks	Allows for contrast statements for all treatment comparisons utilizing all data	9.2.6
	Wilcoxon rank sum tests replaced by ANOVA based on ranks	Allows for contrast statements for all treatment comparisons utilizing all data	9.2.6
	Addition of summary analysis based on Sponsor-defined bacterial pneumonia	Complication of Influenza eCRF not correctly utilized	9.2.7
	Exact Mantel-Haenzel test and Cochran-Mantel-Haenzel test replaced by logistic regression	Allows for contrast statements for all treatment comparisons utilizing all data	9.2.1
	Additional details provided regarding the determination of anaphylaxis and hypersensitivity adverse events	Clarification of existing text	12.1

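### AESIs are counted only from an eCRF field that the SAP never checks against the nine entries the protocol names

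*SAP*

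**What the plan says.** Protocol 9.1.3 introduces its list with "For VIS410, the AESIs include the following" and names nine entries: four gastrointestinal, two skin, hypotension, and two that concern the throat or breathing. Protocol 10.7.1 puts AESIs among the categories to be compared between arms: "The difference in proportions of subjects with AEs, TEAEs, hypersensitivity reaction, anaphylactic reaction, AESIs, and SAEs between treatment groups will be calculated".

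SAP 12.1 gives the analysis definition: "All AESIs will be defined by the eCRF field event type - AESI". The overall summary has a row for TEAEs of special interest and is repeated by region. The definition then passes to the separate AESI table: "The TEAE definitions for these tables will be the same as used in the overall summary of TEAEs".

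Two other event classes are handled differently. For one, SAP 12.1 plans a central review: "Anaphylaxis and hypersensitivity reactions will be determined by clinical evaluation of TEAEs per the Safety Plan prior to database lock". For bacterial pneumonia, SAP 9.2.7 adds a sponsor-derived definition built from medical history, medications and adverse events. The SAP change table gives the reason: "Complication of Influenza eCRF not correctly utilized".

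SAP 16.1, which records departures from the protocol's analyses, does not mention AESIs.

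**The concern.** The protocol describes AESIs by what happened to the patient. The analysis identifies them by how a form was filled in. The two agree only if every event matching a named entry is given the AESI value. The SAP neither assumes this openly nor plans a check of it.

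Omissions lower the AESI proportion in every arm, and they remove most subjects from the arms where the events are most common. Gastrointestinal events were the most common adverse events in earlier VIS410 studies (Protocol 1.5.1.1). SAP 2.4 says that the side-effect profile of each dose will influence dose selection for later studies. An undercount in a comparison the protocol requires therefore bears on a stated use of the trial.

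**Working it through.** **Tracing one event.** Take a TEAE coded to diarrhoea whose event-type field does not hold the AESI value.

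- Protocol 9.1.3: it is a named AESI.
- SAP 12.1, overall summary and its regional repeat: not counted in the AESI row, so not in the difference in proportions.
- SAP 12.1, AESI table (14.3.1.6): not counted, because the same definition applies.
- SAP 12.1, all-TEAE table: counted, since "A summary table by treatment group will present the number and percentage of subjects with TEAEs by SOC and SOC/PT". It also appears in the intensity and relationship tables and in the adverse event listing (16.2.7.1).

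The all-TEAE table does not restore the AESI result. It counts a subject once per class or preferred term, and the nine entries fall across several classes. Adding rows would count some subjects more than once. The number of subjects with any named event would have to be rebuilt from the listing.

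**Size.** The plan states no figure to reproduce, and the documents give neither true AESI rates nor flag completeness. What follows is illustration. Let p_T and p_C be the true proportions of VIS410 and placebo subjects with a recorded named event, and s the fraction of those subjects with at least one such event flagged. If s is the same in all arms:

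flagged difference = s × p_T − s × p_C = s × (p_T − p_C)

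Two sets of rates are used. The first, 30% and 10%, is assumed. The second takes 16.7% from the gastrointestinal event rate with diphenhydramine plus ibuprofen at 2300 mg (Protocol 1.3.3.1; 2/12 = 16.7%) and assumes 5% for placebo. That 16.7% covers gastrointestinal events only, at a dose not used in this trial.

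| True rates | s | VIS410 flagged | Placebo flagged | Difference (points) |
|---|---|---|---|---|
| 30% / 10% | 1 | 30% | 10% | 20 |
| | 0.9 | 27% | 9% | 18 |
| | 0.7 | 21% | 7% | 14 |
| | 0.5 | 15% | 5% | 10 |
| 16.7% / 5% | 1 | 16.7% | 5% | 11.7 |
| | 0.7 | 11.7% | 3.5% | 8.2 |
| | 0.5 | 8.4% | 2.5% | 5.9 |

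In subjects, with 80 on VIS410 and 40 on placebo and s = 0.7:

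- First set: 80 × 0.30 × 0.3 = 7.2 VIS410 and 40 × 0.10 × 0.3 = 1.2 placebo subjects drop out of the AESI count.
- Second set: 80 × 0.167 × 0.3 = 4.0 and 40 × 0.05 × 0.3 = 0.6.

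**Three qualifications.**

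- Under equal s the risk ratio is unchanged (21/7 = 30/10 = 3). Only the proportions and their difference shrink.
- If s differs by arm, the effect on the difference can vary. With 0.9 on VIS410 and 0.7 on placebo the difference is 27 − 7 = 20 points; reversed, it is 21 − 9 = 12.
- A subject is lost only if all of that subject's named events are unflagged. With two events, each flagged independently with probability 0.7, the subject is still counted with probability 1 − 0.3² = 0.91.

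**The case against.** The strongest reply is that the SAP uses the protocol's own data capture. Sites complete the field knowing Protocol 9.1.3, so the field is that definition as applied at the bedside. The eCRF and the Safety Plan are not among the documents, so edit checks or completion guidance may exist unseen. Protocol 12.4.1 provides computerized checks, manual review of listings and queries. Unflagged events stay visible by arm at preferred-term level. The study is exploratory, and its p-values are informational.

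Most of this stands and limits the point. It does not remove it: the cleaning described is general and does not name AESIs, and nothing in the SAP requires the field to agree with the coded terms.

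A reader might infer more than the documents support:

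- *That a fixed list was replaced.* The protocol's wording is inclusive, so the nine entries are named but not closed, and a site may properly flag something else.
- *That the AESI row is the main account of VIS410's toxicity.* The primary safety endpoint is the proportion of subjects with AEs and SAEs.
- *That sites misused the AESI field.* The recorded misuse concerns a different form. It shows that form-based classification can fail in this trial, not that this field did.
- *That about 140 sites for about 120 subjects makes flagging errors likely.* The documents give no distribution of subjects over sites, and sites with no subjects contribute no events.
- *That injection-site events need the same remedy.* The protocol describes those by judgement and gives no term list to map.

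**Conclusion.** The point holds as a gap in specification. SAP 12.1 relies on one eCRF field for AESIs and does not compare it with the entries the protocol names, so incomplete flagging would pass straight into the AESI row, its between-arm difference and the AESI table. The events themselves are not lost from the trial's safety reporting.

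The size is unknown. The factor s follows only if flagging is equally complete in all arms, and the falls from 20 points to 18 or 14 rest on assumed rates and assumed completeness. If flagging is complete, nothing is lost. The case for change is that a safeguard costs little and the SAP already uses comparable ones for hypersensitivity and pneumonia.

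A separate limit remains whichever definition is used. Protocol 9.1.2 states: "The solicited and unsolicited signs and symptoms of influenza will not be reported as AEs". Inclusion criterion 3 counts diarrhea, nausea, vomiting and dyspnea among influenza symptoms. Some events of these kinds may therefore never be recorded as AEs, and no analysis rule can recover them.

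**What to change.** In SAP 12.1, define an AESI as any TEAE that either has a MedDRA preferred term on a list mapped to the nine entries in Protocol 9.1.3, or was given the AESI value by the site. Fix the list before unblinding and attach it to the SAP. Including site-flagged events respects the protocol's open wording.

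Use this definition for the AESI row, the difference in proportions, the regional repeat and the AESI table. List every event where field and term list disagree, and show the flag-only count as supportive. Record the change in SAP 16.1.

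The cost is one preferred-term list to agree, some SAP text and a listing; SAP 12.1 already codes all AEs in MedDRA 20.1. There is a small downside: broad terms such as dyspnoea may bring in illness-related events in all arms. The flag-only count lets a reader see how much that matters.
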